### **Vital Sign Normal Ranges**

Measurement	Normal Range
Body Mass Index	18 – 35 kg/m 
Temperature	95-100 °F (35-37.8 °C)
Diastolic blood pressure	60 – 90 mmHg
Systolic blood pressure	90 – 140 mmHg
Heart rate	50 – 100 bpm
Respiration rate	10 – 25 breaths per minute

### **9.4.     Electrocardiograms**

12-Lead ECGs will be collected at Screening, Week 8 of the Treatment Phase and Week 21-23 of the Post-treatment Phase. Descriptive summaries will be presented for heart rate (bpm), PR interval (msec), QRS duration (msec), uncorrected QT interval (msec) and QTcF (msec). These summaries will be presented by study visit and treatment group.

The number of subjects with ECG results below, within, or above normal ranges, by study visit and to the worst post-baseline will be tabulated (shift tables) for each parameter by treatment group.

Normal, abnormal but not clinically significant, and abnormal and clinically significant ECG investigator interpretation results will be flagged in the listings.

The QT and QTc parameter values will be categorized and flagged for the actual values as:  $\leq 450$  msec,  $450$  msec to  $\leq 480$  msec,  $480$  to  $\leq 500$  msec, and  $>500$  msec and  $\leq 30$  msec,  $30$  msec to  $\leq 60$  msec, and  $>60$  msec for the change from baseline. The number and percent of subjects will be presented by treatment group and visit.

### **9.5.     Physical, Neurological and Eye Examination**

Physical examinations will include assessments of all body systems except genitourinary as well as height and weight and a special assessment for the occurrence of decreased sweating and elevation in body temperature above normal. Neurological examination will include evaluation for impaired reflexes, balance problems, muscle weakness, paresthesia/numbness and tingling, speech difficulties, mental confusion or excessive fatigue. Eye examinations will measure visual acuity and visualize the optic disc through a fundoscopic exam. Subjects will be monitored for visual/ocular disturbances and potential signs of angle closure glaucoma during the participation in the study

Any findings during screening will be recorded as medical history and any clinically significant abnormal findings during treatment will be recorded as an AE. At the EOS physical and neurological examinations, only changes from the screening visit will be noted.

All physical, neurological and eye examination results will be listed.

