The least square mean (LS Mean) of each treatment group (placebo and SPN-538) along with the corresponding standard error, p-values, difference in the LS Mean between SPN-538 and placebo (SPN-538 minus placebo), and 95% CIs will be computed at each visit.

Sensitivity analyses will be performed based on MI, assuming that missing data are MNAR.

Secondary Endpoint Analyses:

Secondary endpoints will be analyzed based on the FAS using appropriate statistical models.

Safety Analyses:

Safety analyses will be performed by treatment group using the Safety Analysis Set. The incidence rate, severity, and relationship to the SM for all AEs will be summarized by treatment group, system organ class (SOC), and preferred term (PT).

Descriptive statistics will be presented for demographics, data from the clinical laboratory test results, vital signs, weight, ECGs, physical, neurological and eye examinations, suicidal ideation, and cognitive assessment.

Inclusion Criteria:

1. Healthy male or female subjects, 6 to 11 years of age (inclusive) at Screening.
2. History of migraine with or without aura conforming to the International Headache Society (IHS) criteria for pediatric subjects (International Classification of Headache Disorders, 3rd edition [ICHD-3]) for at least 6 months prior to Screening.

3. Subjects who experience 3-12 migraine episodes and no more than 14 headache days (migraine and non-migraine) per month during the 3 months prior to Screening and during the 28-day Prospective Baseline Period (based on the Headache Diary).
4. At Screening, a PedMIDAS Disability score of ≥ 20 (indicating at least mild disruption of daily activities) and ≤ 139 (indicating severe disability that may require more comprehensive therapy).
5. Weight of at least 20 kg and no more than 60 kg (inclusive) at the Randomization visit (Visit 3).
6. Considered medically healthy by the Investigator via assessment of physical, neurological and eye examinations, medical history, clinical laboratory tests, vital signs, and ECGs.
7. Able and willing to swallow capsules whole and intact without sprinkling on food, crushing, chewing, cutting, or dissolving before swallowing.
8. Caregiver must be able to read and comprehend written instructions and be willing to supervise the completion of all headache records and questionnaires by the subject as required in the protocol.

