7.11 Safety Analysis

Safety analysis as described below will be conducted using the Safety Analysis Set. All safety analyses will be performed on the Safety Analysis Set.

The incidence rate of AEs will be calculated by treatment group for each System Organ Class (SOC) and Preferred Term (PT). The severity of the AEs and the relationship to

SM will be summarized by treatment group for each SOC and PT. AEs will be summarized using discrete summaries at the subject and event level by SOC and PT, and by severity and relationship separately for each treatment group. Verbatim description and MedDRA SOCs and PTs for all AEs will be contained in the subject data listings.

All AEs occurring after randomization and throughout the study period will be recorded. For subjects who receive SM, TEAEs will be collected starting after the first dose of SM (Visit 3) to the end of the study. These AEs include those that emerge during treatment or worsen in severity during treatment. These AEs will be tabulated, listed and analyzed.

The incidence of AESIs based on AE data will be summarized for each treatment group by MedDRA SOC and PT. Supporting subject listing of AESI will be presented. For AESIs, percentages of subjects experiencing visual/ocular disturbances, oligohydrosis, hyperthermia, metabolic acidosis (serum bicarbonate), hyperammonemia, nephrolithiasis, and hepatic injury will be summarized using descriptive statistics by treatment and collection time point. Clinical laboratory values will be summarized by visit and treatment group using descriptive statistics. For quantitative laboratory parameters, both actual values and change from baseline (values collected at Screening) will be summarized.

Vital signs will be summarized by visit by treatment group using descriptive statistics. Both actual values and change from baseline will be summarized.

ECG results will be summarized by visit by treatment group using descriptive statistics (for quantitative ECG parameters) and frequency tables (for qualitative ECG parameters, including the overall ECG finding).

C-SSRS outcomes will be summarized using number and percent of subjects by categories for suicidal ideation only, suicidal behavior only and suicidality (ideation and behavior combined). The summary will be presented by treatment groups.

For physical, neurological, and eye examinations, change in status from baseline to the EOS will be summarized by body system for each treatment group.

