### 5.3. Safety Variables

The safety endpoints of this study include the following:

1. Incidence of AEs.
2. Clinical laboratory test results (blood chemistry and hematology, urinalysis).
3. Vital signs, physical and neurological examinations, eye exam and ECGs.
4. C-SSRS Assessment.
5. Cognitive Assessment.

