### **9.1. Adverse Events**

All adverse events (AEs) will be coded using the MedDRA Version 24.1.

A treatment-emergent adverse event (TEAE) is defined as an AE with a start date on or after the date of the first dose of study medication, or that worsened in severity following the first dose of study medication. All AEs in this study will be recorded after administration of study medication, therefore all will be considered treatment-emergent.

---

The Investigator is responsible for determining the relationship between the administration of SM and the occurrence of an AE as not suspected or as a suspected reaction to SM. Non-suspected AEs will be those that are determined as not related or unlikely related. Suspected AE are those that are determined as possibly related or definitely related.

Adverse event severity grades are reported as mild, moderate, or severe.

Summaries of incidence rates (frequencies and percentages) of individual TEAEs will be presented by SOC, PT, and treatment group. Such summaries will be displayed for all TEAEs, TEAEs by maximum severity, and TEAEs by relationship.

Each subject will be counted only once within each category level (SOC and PT). If a subject experiences more than 1 TEAE within each category level, the TEAE with the strongest relationship or the maximum severity, as appropriate, will be included in the summaries of relationship and severity. If a particular event is missing the severity and/or relationship, then the strongest possible severity or relationship will be assumed for analysis (severity = severe, relationship = definitely related).

Incidence will be presented by descending frequency of SOC and PT within SOC, and then alphabetically within PT where the incidence is the same; this is based on overall subjects then alphabetically in case of a tie.

In addition, number and percent of patients reporting common AEs ( $\geq 5\%$  in any treatment group) will be presented by PT.

Missing and partially missing AE start and/or stop dates and times will be imputed, for the purpose of statistical analysis, according to the specifications described in Section [6.7.2](#).

In the AE data listings, all AEs will be displayed.

A summary of incidence rates (frequencies and percentages) of TEAEs leading to withdrawal of study medication, by treatment group, SOC, and PT will be prepared for the Safety Population.

Adverse events of special interest (AESI) include the following.

- Metabolic acidosis
- Hyperammonemia

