- Oligohydrosis and hyperthermia
- Clinically significant increase in alkaline phosphatase, creatinine, or eosinophils (specifically, for patients 6 to 11 years, these were noted to be abnormally increased more frequently with TPM than with placebo)
- Clinically significant decrease in total white count or neutrophils
- Visual changes: subjects presenting with blurry vision, ocular pain, and visual field defects subjects must be discontinued early and closely followed to ensure a prompt resolution of ocular AEs.
- Suicidal behavior and ideation

- Cognitive and memory function impairments
- Nephrolithiasis

AESI for AE data will be identified in the AE eCRF page and flagged in the AE dataset. AESI for non-AE data will be identified by Supernus drug safety team based on data listings provided by statistical programming.

The incidence of AESIs based on AE data will be summarized for each treatment group by MedDRA SOC and preferred term. Supporting subject listing of AESI be presented.

A data listing of AEs leading to withdrawal of study medication will also be provided, displaying details of the event(s) captured on the CRF.

Any deaths that occur during the study will be listed. Serious adverse events will be listed and tabulated by SOC and PT and presented by treatment.

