### **10. Changes from Planned Analysis**

There is no change from the planned analyses specified in the protocol.

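### SAP section 9 does not carry the protocol's by-arm examination summary, two of its 11 AESIs or its AESI percentages by time point, while SAP section 10 declares no change; its BMI shift table also applies one fixed range to ages 6-11

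*SAP*

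**What the plan says.** **Examinations.** Protocol 7.11 plans, for the physical, neurological and eye examinations, that "change in status from baseline to the EOS will be summarized by body system for each treatment group". The protocol synopsis agrees: "Descriptive statistics will be presented for demographics, data from the clinical laboratory test results, vital signs, weight, ECGs, physical, neurological and eye examinations". SAP 5.3 names the same examinations as safety variables ("Vital signs, physical and neurological examinations, eye exam and ECGs"). The only output in SAP 9.5 is: "All physical, neurological and eye examination results will be listed".

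**AESIs.** Protocol 6.6.9 lists 11 items that require consistent monitoring. SAP 9.1 opens its list with "Adverse events of special interest (AESI) include the following" and gives nine. On identification it says "AESI for AE data will be identified in the AE eCRF page and flagged in the AE dataset", and on tabulation "The incidence of AESIs based on AE data will be summarized for each treatment group by MedDRA SOC and preferred term". Protocol 7.11 plans that SOC/PT table too. It adds percentages of subjects in seven named categories, by arm and by collection time.

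**BMI.** SAP 9.3 plans shift tables by arm, counting children below, within and above normal at each visit and at the worst post-baseline value. The normal range for BMI is 18-35 kg/m², with no split by age or sex. Protocol 3.3.2 admits ages 6 to 11 and weights of 20 to 60 kg at randomization.

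**Declared changes.** SAP section 10 says: "There is no change from the planned analyses specified in the protocol".

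**The concern.** Safety in this age group is a stated objective of the study, and the examinations are named safety endpoints. A programmer working from SAP section 9 would produce no examination table by arm and no AESI percentages over time. The AESI list in use would be two items shorter than the one given to sites. Section 10 tells a reader that nothing has moved, so the gap could go unnoticed until the study report.

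The BMI table matters because the protocol's Introduction cites weight decrease and negative effects on growth among the known concerns with topiramate. A child who starts in the lowest category cannot move lower, so that child's weight loss does not show as a shift. Here a single fixed bound, blind to age and sex, decides who starts there.

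**Working it through.** **1. Examinations.** Protocol 7.11 asks for a summary by body system and arm; SAP 9.5 gives a listing. Under SAP 9.5 and Protocol 6.8.5, clinically significant findings during treatment are recorded as AEs, so they appear by arm in the TEAE tables of SAP 9.1. What remains without a by-arm comparison is every other change in status.

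**2. AESI lists.** Matched item by item, the nine SAP entries all appear in Protocol 6.6.9. The two protocol items without a match are serious skin reactions and negative effect on growth: 11 - 9 = 2.

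**3. AESI categories over time.** The seven categories of Protocol 7.11, set against the nearest by-arm, by-visit table in the SAP:

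| Protocol 7.11 category | Nearest SAP table |
|---|---|
| Metabolic acidosis | Bicarbonate (SAP 9.2) |
| Hyperammonemia | Ammonia (SAP 9.2) |
| Hepatic injury | Liver tests (SAP 9.2), but no defined category |
| Hyperthermia | Temperature (SAP 9.3) |
| Visual/ocular disturbances | None; eye results listed (SAP 9.5) |
| Oligohydrosis | None |
| Nephrolithiasis | None |

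Four are partly covered by measurements, though not as the percentages the protocol names, and three are not covered over time. Hepatic injury is in neither AESI list.

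**4. BMI lower bound.** A child is 'below' when weight/height² < 18, that is, when height exceeds 100 × √(weight/18) cm:
- 20 kg: 100 × √(20/18) = 105.4 cm
- 25 kg: 100 × √(25/18) = 117.9 cm
- 30 kg: 100 × √(30/18) = 129.1 cm

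**5. BMI upper bound.** 'Above' needs weight > 35 × height². At 60 kg this requires a height under 100 × √(60/35) = 130.9 cm. At 120 cm it requires more than 35 × 1.2² = 50.4 kg, and at 135 cm more than 35 × 1.35² = 63.8 kg, which exceeds the randomization limit.

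**6. Effect on the shift table.** Take two children of 120 cm, height held constant, each losing 10% of body weight:
- 27 kg to 24.3 kg: 27/1.44 = 18.75 to 24.3/1.44 = 16.88, counted as a shift to 'below'.
- 24 kg to 21.6 kg: 24/1.44 = 16.67 to 21.6/1.44 = 15.00, no shift, because the child was 'below' at the start.

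**7. Is SAP section 9 simply out of date?** The SAP's own table of changes records no edit to any part of section 9. The protocol's change log marks its AESI section as a major change. SAP 9.2 still places laboratory tests at every Treatment Phase visit, whereas the current protocol schedule has them after baseline only at Visits 5, 8 and 9. An earlier section that was not updated is the likeliest explanation.

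**The case against.** **Silence is not removal.** The SAP presents itself as adding detail to the protocol and contains no clause giving it precedence. Protocol 7.11 therefore still stands, and section 10 could be read as leaving it in force. That is right as to the protocol's promise. But the SAP as written specifies a listing, and nothing in it prompts anyone to build the missing tables.

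**AESIs are still tabulated by arm.** A reader might infer that the by-arm AESI summary is gone, or that skin and growth events would go uncounted. The documents do not support either. SAP 9.1 keeps incidence by arm by SOC and PT, driven by an eCRF flag rather than by its own list. Protocol 6.6.9 tells sites to report all 11 items within 24 hours. The sponsor's drug safety team identifies non-AE AESIs from listings, and AEs of any kind reach the TEAE tables. What stands is narrower: the two lists disagree, and the time-point percentages are missing.

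**The missing items may be a copying matter.** They would sit where the SAP list appears to run over a page, so the signed copy should be checked. The examination and time-point gaps do not depend on this.

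**BMI is not a departure.** Protocol 7.11 promises only descriptive vital-sign summaries, and the shift table is the SAP's addition. Any three-category table has a floor, and the continuous weight and BMI summaries in SAP 9.3 are unaffected. A reader might infer that most children are misclassified, but the documents give no heights and cannot show this. The objection to a fixed bound for ages 6 to 11 stands.

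**Height.** A reader might also take the lack of a by-visit height table as a broken promise. Protocol 7.11 plans no such table.

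**Conclusion.** The point holds and should be corrected before database lock. SAP section 10 is inaccurate on two matters: the examination-status summary, which is absent, and the AESI plan, which is incomplete by 2 of 11 listed items and by the seven-category percentages over time. The practical AESI loss falls mainly on visual/ocular disturbances, oligohydrosis, nephrolithiasis and a defined hepatic-injury category.

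The BMI range is a separate weakness of design. Its cut-offs follow from arithmetic alone. The share of children affected is unknown, and the upper-bound result assumes weights stay at or below 60 kg, a limit that applies only at randomization.

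All of these outputs are descriptive. SAP section 9 plans no inferential safety tests, and no efficacy conclusion changes.

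**What to change.** - **SAP 9.5:** add the Protocol 7.11 summary of examination status at end of study against baseline, by body system and arm.
- **SAP 9.1:** bring the AESI list to the 11 items of Protocol 6.6.9. Restore the percentages for the seven categories by arm and collection time, and state where hepatic injury belongs and how it is defined.
- **SAP 9.3:** replace the 18-35 kg/m² range in the shift table with age- and sex-specific categories, naming the reference used.

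The first two changes would make the section 10 statement true on these points. The cost is SAP wording and table programming. The data are already collected: physical and neurological examinations at Screening and Visit 9 among others, eye examinations at Visits 3, 6 and 9, and weight and height at the physical examinations. The BMI change also requires choosing a growth reference, which the documents do not supply. No visit, sample size or efficacy analysis changes.

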#### **9.6. Columbia Suicide Severity Rating Scale (C-SSRS)**

Assessment of suicidal ideation and behavior will be conducted using the Columbia-Suicide Severity Rating Scale (C-SSRS) which classifies suicidal ideation and behavior events into 11 preferred categories including 5 levels of suicidal ideation, 5 levels of suicidal behavior, and the category of self-injurious behaviors with no suicidal intent. The C-SSRS will be performed at all study visits. At the Screening visit, the “baseline” version of the C-SSRS will be administered. This version assesses Suicidal Ideation and Suicidal Behavior during the subject’s lifetime and during the past 6 months. At the subsequent study visits, the “since last visit” version will be administered.

The number and percentages of subjects with a response of “Yes” at any point on the suicidal ideation only, suicidal behavior only, and suicidality (ideation and behavior combined) items will be summarized by treatment group.

#### **9.7. Cognitive Assessment**

Cognitive function will be assessed by evaluating the responses to the cognitive questionnaire to which the subjects replied. Responses to the questions will be presented in subject listing and summarized by study visit and treatment group.

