Note: Non-pharmacologic approaches involving lifestyle modifications (e.g., trigger factor avoidance, stress reduction techniques, regular exercise, and good sleep hygiene) will be allowed as long as they were started at least 1 month prior to Screening and are continued throughout the study.
10. Currently on a ketogenic diet, or on a ketogenic diet within 6 months prior to Screening.
11. Significant major psychiatric disorder (e.g., psychosis, bipolar disorder, major depression and generalized anxiety disorders), or documented developmental delays or impairments (e.g., autism, cerebral palsy, or mental retardation) that, in the opinion of the Investigator, would interfere with adherence to study requirements or safe participation in the trial.
Note: Subjects with an established diagnosis of Attention Deficit Hyperactivity Disorder (ADHD), will be allowed if they are taking a stable dose (7 days/week) of ADHD stimulant medication (extended or controlled release) for at least 12 weeks prior to the Screening visit and refrain from changing the dose or the ADHD medication during the study duration.
12. Subjects with seizures or a history of seizure-like events within 6 months prior to Screening, or a history of seizure disorder within the immediate family (siblings, parents).
13. Known history of visual field defects regardless of etiology.
14. Presence of active liver disease (including baseline serum ammonia levels >2 times the upper limit of normal).
15. Abnormal kidney function, subjects undergoing hemodialysis, or subjects with a history of nephrolithiasis.
16. Known neurological disorder or a structural disorder of the brain from birth; head trauma or infectious disease resulting in migraine or worsening of migraine symptoms; or previous central nervous system (CNS) surgery.

17. Known history of uncontrolled asthma, uncontrolled diabetes, arrhythmias or congenital heart disease.
18. Evidence of suicidal ideation and/or suicidal behaviors within 6 months prior to Screening or during the Pre-treatment phase.
19. Pregnancy, breastfeeding, or refusal to practice abstinence or acceptable birth control during the study for FOCPs.
20. Known history of substance-use disorder according to the Diagnostic and Statistical Manual of Mental Disorders 5th Edition (DSM-5) or used alcohol or illicit drugs in the 3 months prior Screening.
21. Any other reason that could interfere with the subject's participation in the study as determined by the Investigator.

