6.8.7 Cognitive Assessment

Cognition refers to the mental processes involved in gaining knowledge and comprehension such as thinking, knowing, remembering, judging, and problem solving. These higher-level functions of the brain encompass language, imagination, perception, and the planning and execution of complex behaviors. Monitoring for cognitive/neuropsychiatric effects is recommended as part of standard clinical practice in TPM use ("[National Institutes of Health-DailyMed- Trokendi XR- Prescribing Information.](#)" 2022). The sponsor created a checklist ([Appendix 10.5](#)) of questions related to the subject's daily activities; subjects are asked to rate each question on a scale from 0 to 3 where 0 means never and 3 very often based on his/her recollection of the past weeks since the last visit. It is recommended to conduct the assessment with the parent(s) first. If discrepancies are found between different sources of information, the study staff will have to use their best clinical judgement.

Changes in cognitive function will be assessed at Visit 3, Visits 5 through 9 and at the safety follow-up phone call after the EOS.

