### 3.5. Sample Size and Power Considerations

Based on data from previous studies conducted in adolescents and adults (MIGR-001, MIGR-002 and MIGR-003), a common SD of 3 is assumed for both the treatment and control group. Assuming a treatment difference of 1.1, a sample size of 117 subjects per arm (a total of 234 subjects) will yield 80% power to detect a non-zero difference in the mean change from baseline in the monthly migraine days between the SPN-538 and the placebo groups using a two-sample t-test at a 2-sided significance level of alpha=0.05.

Assuming that approximately 15% of subjects will drop-out before completing the study, a total sample size of 276 subjects (138 subjects per arm) will be randomized in the study.

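### The cognitive questionnaire is summarised only as answers by visit and arm, with no within-child comparison with the pre-dose Visit 3 answers

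*SAP*

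**What the plan says.** SAP 9.7 gives the whole planned analysis of the questionnaire: "Responses to the questions will be presented in subject listing and summarized by study visit and treatment group". Protocol 7.11 uses the same words. Both texts are intact, so redaction does not explain what is absent.

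Protocol 6.8.7 states a different aim: "Changes in cognitive function will be assessed at Visit 3, Visits 5 through 9", and again at the safety follow-up call. The form (Protocol Appendix 10.5) has seven questions, the last in three parts, so nine responses. Each is scored 0 to 3 for the time since the last visit. There is no total score and no threshold.

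SAP section 4 defines both baseline (the last non-missing value before first dose) and change from baseline. These are applied to other safety measures:

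- laboratory tests (SAP 9.2) and vital signs (9.3): change from baseline, and shift tables that include the worst post-baseline value;
- ECGs (9.4): shift tables, and categories of QT change;
- physical, neurological and eye examinations (Protocol 7.11): change in status from baseline to end of study, although SAP 9.5 only lists them.

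**The concern.** Cognitive assessment is a named safety objective and endpoint. Protocol section 1 treats cognitive monitoring as crucial and places the higher risk in exactly the age group enrolled.

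The questions concern memory, attention, tiredness and slowing. Some children will answer above zero before any dose, not least because of the eligibility note: "Subjects with an established diagnosis of Attention Deficit Hyperactivity Disorder (ADHD), will be allowed", on a stable stimulant dose. A table of answers at one post-baseline visit counts a child who moved from 0 to 3 in the same cell as a child who was at 3 throughout. What is at stake is how clearly the report can show how many children became worse, and by how much, in each arm.

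**Working it through.** **Arm size.** The documents give no figure for the cognitive endpoint, so the only stated figure to reproduce is the arm size. SAP 3.5 gives "Assuming a treatment difference of 1.1", "a common SD of 3 is assumed for both the treatment and control group" and "a sample size of 117 subjects per arm (a total of 234 subjects) will yield 80% power", "using a two-sample t-test at a 2-sided significance level of alpha=0.05". With the normal approximation, n = 2 × (1.960 + 0.842)² × 3² / 1.1² = 116.8, so 117 per arm. Allowing for dropout, 234 / 0.85 = 275.3, so 276 randomized and 138 per arm. Both match the SAP.

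**Model.** Let b be the proportion with a complaint at Visit 3, assumed to persist, and p the proportion newly impaired among children free of it at Visit 3.

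- Raw by-visit proportion = b + (1 − b)p
- New impairment among all children in the arm = (1 − b)p
- SE = √[(q₁(1 − q₁) + q₀(1 − q₀)) / 138], where q₁ and q₀ are the drug and placebo proportions in the table concerned
- z = difference / SE, used only as an index of signal

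The absolute difference is (1 − b)(p₁ − p₀) in both tables. It is therefore unchanged as long as both use all children as the denominator.

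**Numbers.** Assumed, not from the documents: p = 10% on drug and 2% on placebo, b = 10% to 30%.

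| b | Raw, drug vs placebo | Ratio | SE (points) | z | New, drug vs placebo | Ratio | SE (points) | z | Difference (points), both tables |
|---|---|---|---|---|---|---|---|---|---|
| 10% | 19.0% vs 11.8% | 1.61 | 4.3 | 1.67 | 9.0% vs 1.8% | 5.0 | 2.7 | 2.68 | 7.2 |
| 20% | 28.0% vs 21.6% | 1.30 | 5.2 | 1.23 | 8.0% vs 1.6% | 5.0 | 2.5 | 2.52 | 6.4 |
| 30% | 37.0% vs 31.4% | 1.18 | 5.7 | 0.98 | 7.0% vs 1.4% | 5.0 | 2.4 | 2.34 | 5.6 |

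At b = 0 the two tables are identical. SAP 3.5 also assumes dropout: "approximately 15% of subjects will drop-out before completing the study, a total sample size of 276 subjects (138 subjects per arm) will be randomized". With 117 per arm, every z is multiplied by √(117/138) = 0.92, and the contrast between the tables is the same.

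**Other assumed rates.** With p = 15% vs 5% and b = 30%, the raw table shows 40.5% vs 33.5% (ratio 1.21, SE 5.8 points). New impairment is 10.5% vs 3.5% (ratio 3.0, SE 3.0 points). The difference is 7.0 points in both.

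**If complaints can resolve.** Keep those rates but let only 70% of baseline complaints persist. The raw proportion is then 0.7b + (1 − b)p: 31.5% on drug and 24.5% on placebo, from 30% in each arm at Visit 3. The drug arm appears to rise by 1.5 points although 10.5% of its children are newly impaired, because resolved complaints offset new ones. The 7.0-point difference between arms survives, but the number who worsened cannot be read from the table.

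**The case against.** The case against making much of this is strong in several respects.

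- **The comparison between arms is sound.** Visit 3 is among the summarised visits, so each arm's pre-dose distribution stands beside the later ones, and 1:1 randomization balances earlier complaints on average. A reader might infer that impairment on drug is buried or biased away. The documents do not support that.
- **The absolute difference does not shrink.** Setting 6.4 points in the raw table against 10% vs 2%, or 8 points, changes the denominator from all children to those unaffected at Visit 3. On one denominator it is 6.4 points both ways.
- **There is a second route.** Cognitive and memory impairment is an adverse event of special interest, reportable within 24 hours (Protocol 6.6.9) and summarised by arm (SAP 9.1). So it would be wrong to infer that cognitive harm is otherwise unexamined. But no rule links a worsened answer to an adverse event. SAP 9.1 lets the drug safety team identify such events in non-AE data from listings, but it gives no criterion, and the planned incidence table covers AE data only.
- **The individual data are listed.** True, but a listing is not a summary by arm, and it leaves the definition of worsening to be chosen later.
- **Other measures are not uniformly handled.** The C-SSRS has no baseline contrast (SAP 9.6), and laboratory and vital-sign shifts rest on normal ranges that this checklist lacks. Two questions (5 and 6) already hint at change in their wording. This weakens the argument from consistency, but it does not answer Protocol 6.8.7.

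What stands is the omission itself: marginal columns show net levels, not who worsened.

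**Conclusion.** The omission is confirmed. The protocol says changes in cognitive function will be assessed, a pre-dose questionnaire is collected, and the planned summary does not compare a child with his or her own Visit 3 answers.

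The consequence is loss of clarity, not bias. In the illustration the ratio between arms falls from 5.0 to between 1.6 and 1.2, and the SE is about 1.6 to 2.4 times as large. The signal index is about 1.7 to 1.0 raw against 2.7 to 2.3 for new impairment. These figures rest on assumed background and new-impairment rates and, in the main table, on complaints that persist. They are not predictions. SAP section 9 plans no inferential tests for safety, so z measures only how clearly a difference would stand out. With few pre-existing complaints, the loss is small.

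**What to change.** In SAP 9.7 add, descriptively, for each of the nine responses (7a, 7b and 7c separately) and by arm:

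- a shift table from Visit 3 to each later visit and to the worst post-baseline value;
- the number and percent worsening by at least 1 and by at least 2 categories, among all Safety Analysis Set children with a Visit 3 answer and any post-dose answer;
- a statement that the pre-dose Visit 3 answer is the baseline, with a count of children who lack one.

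Two details matter.

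- **Early termination.** These assessments must enter the worst value. The questionnaire is not given at Visit 4, and children who stop early complete the Visit 9 procedures (Protocol 3.4.1, 3.4.2). A child who stops before Visit 5 therefore has the only on-site post-dose answers at that visit. A worst value limited to Visits 5 to 8 would drop that child.
- **Visit 9 and the follow-up call.** Scheduled Visit 9 should be a taper-period column, not an off-drug one, because its recall runs back to Visit 8 and drug is still taken during the taper. The follow-up call should be a separate post-treatment column. The SAP should also say whether either feeds the worst value.

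No new data or visits are needed. The cost is SAP wording before database lock and several tables, given nine responses. Taking the worst of several visits against a single baseline will raise apparent worsening in both arms through ordinary fluctuation, so those rows must be read against placebo. The category cut-offs are a convention, because the checklist has no validated threshold in the documents; fixing them before unblinding is the point.
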